5.2 Recruitment Methods

See Section 5.1

5.3 Informed Consent Procedures

The informed consent process will be conducted over the telephone by IRB approved research staff who have experience consenting Veterans for intervention studies within VHA. Following the informed consent discussion using the IRB approved informed consent document, Veterans interested in participating in the study will be asked to complete and sign informed consent document and HIPAA authorization forms via the approved methods described below, according to their preference and access to email, printing, and scanning. For CAVHS Veterans

enrolled in the study, the informed consent and HIPAA authorization documents will be scanned into CPRS. A research flag and enrollment note will be entered into CPRS. This note will include identification of the IRB approved mechanism used to obtain documentation of informed consent.

Study staff will obtain documentation of informed consent and HIPAA authorization from individuals who are interested in participating in one of 3 ways: Return-by-Mail, Return-by-Digital Image Capture, Return-by-DocuSign

For Minneapolis study participants, CAVHS research staff will access the study participant's Minneapolis CPRS medical record and create a CWAD posting to include the CAVHS IRB required research flag information. Additionally, study staff will enter a progress note to include templated information required in CAVHS participants' enrollment note adding the study participant's primary care provider (PCP) as an additional signer. This will serve as a mechanism to specifically notify the PCP that the Veteran is participating in the study.

5.3.1 Return by DocuSign. DocuSign is a VA cloud Software as a Service (SaaS) solution approved for use in VA research for the purpose of sending digital documents to patients and collection of their signatures. After completing screening questions, the study team contact will send a DocuSign envelope (email containing links to the study documents) to interested potential participants. The email will contain a reminder for the recipient to not sign the documents prior to the scheduled contact time to review the documents and have questions answered.

5.3.2 Return-by-Mail. Veterans who are interested in participating in the study and who have, or can print, or can receive a faxed copy of the informed consent and HIPAA authorization forms may complete, sign and date these forms and return them to the study team in the provided postage paid envelope. Upon receipt, the study team member who conducted the informed consent process will countersign the ICF and return copies of the ICF and HIPAA authorization to the Veteran via mail. The baseline interview may be initiated after receipt of the signed ICF and HIPAA documents by the study team.

5.3.4 Return-by-Digital Image Capture. Veterans who are interested in participating in the study and who have, or can print, or can receive a faxed copy of the informed consent and HIPAA authorization forms may complete, sign and date these forms and return via: **Email** by scanning the digital image or photos of the completed pages of the ICF and HIPAA Authorization forms and sending the images back to the research team via a VA Outlook account, using their personal email account or **Text Message** via cell phone. Veterans using email will be encouraged to use Azure RMS to securely transmit scanned pictures and images back to the study team, however, they cannot be required to use Azure RMS to return documents to the study team.

Veterans who choose to use their personal computers or phones to send images of their consent/ HIPAA documents to the study team via text or unencrypted e-mail, will be told (prior to sending the images) that there is a risk when sending sensitive information in an insecure manner. Study staff will advise participants to retain the signed copies of their ICF and HIPAA Authorization forms for their records and recommend that they delete the emails/texts from their sent items after sending.

Upon receipt, the study team member who conducted the informed consent process will countersign the ICF. The baseline interview may be initiated after receipt of the signed ICF and HIPAA documents by the study team.

5.4 Inclusion/Exclusion Criteria

See Section 5.1

5.5 Study Evaluations

We preregistered two primary outcomes: **cessation of benzodiazepines and dose reduction of benzodiazepines at six-month follow-up**. Cessation will be defined as the absence of a benzodiazepine prescription renewal in the six months prior to follow-up, and dose reduction will be defined as a 25% or greater decrease in benzodiazepine use that has been sustained for three months or more at follow-up. Cessation will be defined as an absence of a benzodiazepine prescription at the time of the 6-month follow-up that was sustained for three consecutive months or more. Dose reduction will be defined as a 25% or greater reduction compared with baseline sustained for three consecutive months or more. All participants who cease benzodiazepines entirely will be included in those who achieve 25% or more reduction.

Assessment of reduction in benzodiazepine use to include differing doses will be converted to lorazepam equivalents and the baseline dose will be defined as the average daily dose in the six-months prior to randomization. These data will be obtained from the CDW. We will also collect participants' self-report data on benzodiazepine use, using a six-month Timeline Followback (TLFB) method (National Institute on Drug Abuse, 2021 [18], to determine the existence of any additional benzodiazepine prescriptions (e.g., from a non-VHA provider) and/or whether any additional benzodiazepine use occurred between baseline and six-month follow-up that was not captured in the administrative data at baseline and six-month follow-up. TLFB is a valid calendar-based method that asks participants to retrospectively recall their drug use (e.g., yes, or no, daily dose) up to two years prior to the interview date (see Appendix B for copy of TLFB).

It is true that CDW prescription medication fill records may not always accurately reflect changes in Veterans' consumption of their medication. Also true is that self-report of medication use is not always accurate. Because all methods for assessing medication use have advantages and disadvantages, we will collect data both from the CDW and the TLFB and we will look at both to determine the outcome.

Pre-registered secondary outcomes are **anxiety symptoms, sleep quality, and overall health and quality of life**. Anxiety symptoms will be measured by the Generalized Anxiety Disorder Scale (Spitzer et al., 2006) [19] (see Appendix C for copy of GAD-7). This seven-item scale asks about the presence and severity of seven symptoms of anxiety (e.g., feeling on edge, having trouble relaxing) and includes an omnibus item rating that is the extent to which any of the seven symptoms has made it difficult "to do your work, take care of things at home, or get along with other people". Items can be summed for an overall rating of anxiety symptoms. Sleep quality will be measured by the Patient-Reported Outcomes Measurement System brief sleep disturbance scale (Yu et al., 2012) [20]. This eight-item scale assesses degree of difficulty falling asleep, degree to which sleep is refreshing, and ability to stay asleep through the night. Items are summed to indicate symptom severity (see Appendix D for copy of sleep assessment).

Overall health and quality of life will be measured by the RAND Veterans Short Form-12 measure (Schalet, 2015) [21], which comprises items assessing global emotional and physical well-being and function (e.g., "How much time in the past four weeks did you have a lot of

energy?", "Compared to one year ago, how would you rate your physical health today?") (see Appendix E for copy of VR-12 form). The final secondary outcome is cessation, or 25% decrease of benzodiazepine use at 12 months; unlike the prior measurements, this will be conducted using databases only.

We will also be assessing participants alcohol use using the three-item Alcohol Use Disorders Identification Test-consumption items, readiness to change medication use using the Readiness Rule, and symptoms of benzodiazepine dependence using the Severity of Dependence Scale. These tools/scales are included in the baseline and 6-month follow-up assessments. Veteran participants will provide self-report of this information for these measures, during their baseline and 6-month interviews.

To determine whether any intervention effects on benzodiazepine use evident at six-months follow-up are maintained, data on benzodiazepine use will again be gathered at 12-month follow-up using VHA centralized databases only (resource constraints prevent assessing this by interview). No other 12-month outcome data will be gathered.

Participant outreach: To conduct 6-month follow up assessments, study staff will attempt to contact Veterans by phone for three months following the date in which their 6-month follow-up was due. We are using this approach because it has worked well in terms of contacting follow-ups in our prior randomized controlled trials. Should the participant state they no longer wish to participate, study staff will document and no further attempts to contact the participant will be made. In our experience, Veterans appreciate attempts to reach them and do not get upset by these multiple attempts.

Should we not be able to reach the person by phone during this 3-month period following the date of the 6-month assessment, we plan to mail the 6-month assessment to the participant. The goal of this mailing is to obtain data from participants who would be otherwise lost to follow up. This is important to do in an intent to treat analysis as we want to make efforts to collect data from all study participants. We have used this approach in previous studies and have been able to obtain data from participants we might have otherwise categorized as lost to follow-up. Should the participant not respond to outreach efforts they will be considered lost to follow up.

EMPOWER website utilization: The EMPOWER website will also include Google Analytics which will anonymously track the number of independent users of the site along with the number of visits. We have also added a question to the 6-month follow-up asking participants if they accessed the EMPOWER website in the prior 6-months.

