Aim 1 has been completed. A promising non-VA benzodiazepine cessation intervention (EMPOWER) has been converted from paper & pencil to an electronic format tailored to Veterans. Aim 2, conduct a **randomized clinical trial of the effectiveness of the tailored, electronic intervention (EMPOWER for Veterans) on VA primary care patients' benzodiazepine cessation/reduction and functional outcomes is being implemented**. A third aim will seek to conduct a budget impact analysis to estimate the costs of implementing EMPOWER for Veterans throughout VA. The Palo Alto, CA site will conduct Aim 3 and thus seek approval for related study activities at their site. **This protocol seeks approval for Aim 2 of this research study.**

Innovation

Converting the effective use of the paper-and-pencil version of EMPOWER to an electronic version that works on smart phones, tablets, and/or desktop computers, the proposed project intends to tailor the electronic version (EMPOWER for Veterans) to the needs and preferences of the Veteran population; in effect reducing risks among this population of benzodiazepine users.

Methodology

When EMPOWER for Veterans is fully designed, its effectiveness will be evaluated in a two-arm individually randomized controlled trial with 170 Veterans at the Central Arkansas Veterans Healthcare system and the Minneapolis VA Health Care System, and affiliated sites. Veterans who have been taking benzodiazepines for at least 3 months and have access to a smartphone or desktop/laptop computer will be invited to participate. The primary hypothesis of the study is that Veterans receiving EMPOWER for Veterans will be significantly more likely to cease benzodiazepine use entirely and reduce their dose by at least 25% at 6-month follow-up than the control group. The secondary hypothesis is that Veterans receiving EMPOWER for Veterans will also experience fewer anxiety symptoms, better sleep quality, and overall health/quality of

life at 6-month follow-up. A supplemental analysis of benzodiazepine use only will be conducted at 12 months, using VA databases to evaluate whether changes identified persist over time.

Impact

Considering that electronically delivered interventions are inexpensive to disseminate once they have been developed, this project has an excellent chance to promote health care value by creating an easily scaled-up, method of reducing the prevalence of the widespread risk of long-term benzodiazepine use to improve Veterans' health.

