To tailor EMPOWER to the veteran population, our research team worked with VHA patients, physicians, and administrators; we then worked with software developers to convert the intervention to a computer-delivered format we call EMPOWER for Veterans (Electronic Version). This protocol describes how EMPOWER for Veterans will be tested in a randomized clinical trial evaluating whether it is effective with a markedly different population and format than in the initial Canadian study. The primary hypotheses of the RCT are that long-term users of benzodiazepines who are assigned to receive EMPOWER for Veterans will be significantly more likely than controls to cease taking benzodiazepines or reduce their benzodiazepine dose by at least 25% at six-month follow-up. The secondary hypotheses are that relative to controls, participants receiving EMPOWER for Veterans will improve more on anxiety symptoms, sleep quality, and overall health/quality of life at six-month follow-up. As functional outcomes were not measured in the original EMPOWER study, this is a unique contribution of the present trial. In addition to being important in themselves, these three secondary outcomes may moderate or mediate participants' response to EMPOWER for Veterans. For example, if secondary outcomes improve upon benzodiazepine tapering, participants may be more likely to continue to full cessation. In contrast, if functional outcomes deteriorate, patients and their physicians may be inclined to abandon EMPOWER for Veterans; if this were a common result it would likely reduce the adoption of EMPOWER for Veterans within VHA. Also, part of our secondary analysis will be to explore whether any effects of EMPOWER for Veterans observed on our primary outcomes at six-month follow-up are maintained at 12-month follow-up.

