3.0 Objectives

The overall goal of this project is to create an electronic version of EMPOWER tailored to Veterans receiving VHA primary care. Specifically, this study maintains three aims. This protocol is specific to Aim 2, which is described in detail as the following:

Aim 2: Conduct a randomized clinical trial to test the effectiveness of the tailored, electronic intervention (EMPOWER for Veterans) on VA primary care patients' benzodiazepine cessation/reduction and functional outcomes at follow-up.

The primary hypotheses of Aim 2 are that in a clinical trial of 170 Veterans who are long-term users of benzodiazepines, those receiving the EMPOWER for Veterans intervention will be significantly more likely at 6-month follow-up to (a) cease taking benzodiazepines entirely, and (b) reduce their benzodiazepine dose by 25% or more. A secondary hypothesis of Aim 2 is that, relative to controls, Veterans receiving EMPOWER for Veterans will improve more on three functional outcomes: anxiety, sleep quality, and overall health/quality of life.

This protocol only describes Aim 2 research activities, which will occur at the Central Arkansas Veterans Health Care System; and as a result, IRB approval is being requested to conduct Aim 2 only.

We plan to request approval for Aim 3 at the Palo Alto Veterans Healthcare System, since the work for that aim will be conducted at that site.

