Study staff will send an unencrypted email with instructions from the User Guide for External Azure RMS Recipients first to confirm the Veteran’s email address and help recipient to open the email message. Study team will then send a second email with the informed consent and HIPAA authorization documents attached, which will include instructions on how to securely transmit pictures or scanned images using RMS.

Once the potential participant has available hard copy or DocuSign informed consent and HIPAA authorization documents, the study staff will review the study purposes, procedures, risk, and benefits and allow time for questions. Study staff will inform Veterans that if they are assigned to the EMPOWER condition, they may voluntarily choose to taper their benzodiazepines; however, this is not required to participate in the study. This is also stated on the EMPOWER website.

Participate Compensation:

Veterans will be compensated for their time, checks for \$30 will be mailed to them 4-6 weeks after completing the baseline and 6-month assessments. Participants who complete both the baseline and 6-month assessments will receive a total of \$60.

Sample Size

The original EMPOWER study reported a more than five-fold difference in benzodiazepine cessation and reduction rates with an OR greater than 8, which converts to a Cohen’s d greater than 0.8 Tannenbaum et al., 2014) [15]. However, we powered the present study using a more conservative estimate of the intervention effect based on a recent meta-analysis of 17 clinical trials (Boumparis et al., 2017) [17] showing that computer-delivered interventions demonstrate an effect size on drug use only somewhat lower than medium (0.36).

To attain 80% power with .05 type I error rate to detect a medium effect size of 0.35 with intra-class coefficient of .008 (based on the original EMPOWER study; Tannenbaum et al., 2014) [15] for the primary outcomes of benzodiazepine cessation/reduction, 66 patients per group will be needed. Assuming an 80% six-month follow-up rate, this will require enrollment at baseline of

170 participants (i.e., 85 per group). All data will be analyzed by the study biostatistician ([name]).

Randomization

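### Two nested primary outcomes share one .05 error rate and one 80% power, and the plan never says whether success needs either outcome or both

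*Combined protocol and SAP*

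**What the plan says.** Section 5.5 (Study Evaluations): "We preregistered two primary outcomes", cessation and dose reduction, both at six months. It makes them nested: "All participants who cease benzodiazepines entirely will be included in those who achieve 25% or more reduction".

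The hypotheses are worded in three ways:

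- Abstract, Methodology: one hypothesis in the singular ("The primary hypothesis of the study is that Veterans receiving EMPOWER for Veterans will be significantly more likely"), joined by *and*: "significantly more likely to cease benzodiazepine use entirely and reduce their dose by at least 25% at 6-month follow-up".
- Section 3.0 (Objectives): plural hypotheses, listed as "a) cease taking benzodiazepines entirely, and (b) reduce their benzodiazepine dose by 25% or more".
- Section 2.0 (Introduction): plural hypotheses, joined by *or*: "significantly more likely than controls to cease taking benzodiazepines or reduce their benzodiazepine dose by at least 25% at six-month follow-up".

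Section 5.1 (Sample Size) begins "To attain 80% power with .05 type I error rate" and gives a single figure, 66 per group, for the primary outcomes together. It does not say whether the .05 is one- or two-sided. Section 5.6 (Data Analysis) models both outcomes. It gives no testing order, no split of alpha and no both-required rule. The only significance level in that section is the 0.05 for dropping the arm-by-time interaction.

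**The concern.** The criterion for a positive trial is not fixed. Suppose one outcome is significant at six months and the other is not. Under the *or* wording that could be reported as success, and under the *and* wording as failure. Nothing in section 5.6 settles it, so the choice could be made after the results are known.

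The two readings also break different parts of the sample size statement. If either outcome suffices, two tests at .05 do not hold an overall .05. If both are needed, the error is controlled, but the chance of success is below the 80% stated for a single test.

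**Working it through.** **1. Inputs from the plan.** Two primary outcomes, cessation nested in reduction (5.5). Alpha .05, power 80%, effect size 0.35, 66 per group after 80% follow-up, 85 per group enrolled (5.1).

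**2. Inputs assumed.** The plan gives no control rates and no sidedness. I take two-sided .05, which is .025 in the direction of benefit for each outcome, with null cessation of 5-27% and null reduction of 13-40%. The test is an unadjusted 6-month comparison (pooled two-proportion z), which simplifies the covariate-adjusted repeated-measures model in 5.6.

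**3. The plan's own figure.** For a standardised difference of 0.35, n = 2(1.960 + 0.842)²/0.35² = 129 per arm, not 66. Power at 66 is Φ(0.35√33 − 1.960) = Φ(0.05) = 52%. This gap is a separate problem, not caused by multiplicity, and the error rates below barely depend on n. For dropout, 66/0.8 = 82.5, so 83 per arm or 166 in total, close to the 170 stated.

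**4. Either outcome suffices.** With null cessation rate c and reduction rate d, nesting gives the correlation r = √[c(1−d)/(d(1−c))]. For c = 10%, d = 30%: r = √(0.07/0.27) = 0.51. The large-sample chance of at least one false claim of benefit is 1 − Φ₂(1.96, 1.96; r).

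| Null cessation, reduction | r | Large-sample: benefit / any rejection | 66 per arm: benefit / any rejection |
|---|---|---|---|
| 5%, 40% | .28 | 4.8% / 9.5% | 4.6% / 9.3% |
| 5%, 20% | .46 | 4.6% / 9.2% | 4.4% / 8.9% |
| 10%, 30% | .51 | 4.5% / 9.1% | 4.6% / 9.1% |
| 20%, 40% | .61 | 4.4% / 8.7% | 4.3% / 8.6% |
| 20%, 25% | .87 | 3.7% / 7.3% | 3.6% / 7.2% |
| 18%, 20% | .94 | 3.3% / 6.6% | 3.2% / 6.4% |

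The last column is exact enumeration, except the 18%, 20% row, which is simulated with 400,000 trials. The limits for any rejection are 5% if the outcomes coincide and 1 − 0.95² = 9.75% if they are independent.

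**5. Rare cessation.** With null cessation of 1% and reduction of 5-10%, the pooled test on cessation rarely rejects, and the false-benefit rate is 2.5-2.9%.

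**6. Both required.** If neither outcome is affected, the false-benefit rate is 0.2-1.8% (any direction 0.4-3.6%). The worst case is a very large effect on reduction and none on cessation: any-direction error 4.8-5.1%, benefit 2.4-2.5%, so about the nominal level.

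For power, take treatment rates that give each outcome 80% at 66 per arm. From 10% and 30% these are 28.9% and 54.0%, and the chance that both are significant is 69%. Over eight assumed pairs of control rates it is 68-73%.

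**7. Holm.** Under the assumptions of steps 2 and 4, the false-benefit rate is 1.7-2.4% and any rejection 3.4-4.8%. Under the effects of step 6, one outcome tested at .025 has 71-75% power, and at least one outcome succeeds in 81-87%.

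**The case against.** The strongest reply is that *and* in the Abstract and the Objectives means both, so nothing is inflated. On that reading there is indeed no inflation. But section 2.0 says *or*, no section states a both-required rule, and section 5.1 gives no power for winning on both. The plan is still incomplete, on power rather than error.

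A second reply is that the outcomes are strongly correlated, so any excess is trivial. The nesting is already in the calculation. The lowest values need almost every reducer to be a ceaser.

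A third is that two separately reported hypotheses need no adjustment. Practice does differ on this. But section 5.1 attaches one .05 to the two outcomes together, and unadjusted tests with either sufficing do not in general keep that figure. If .05 per outcome was meant, the plan should say so and disclose the joint rate.

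Three stronger inferences are tempting, and the documents do not support them:

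- *That the error rate is inflated as the plan stands.* It is inflated only if either outcome may be claimed alone, which the plan neither permits nor excludes.
- *That 3.2-4.8% bounds the false-benefit rate.* It depends on assumed null rates. Section 5.5 gives two differing definitions of cessation, and a stricter one could make control cessation rare enough to remove most of the excess. In the other direction, null rates of 10% and 50% with 85 per arm give 4.95%.
- *That the plan may intend a patient-level composite.* Given the nesting, a patient-level *or* is just reduction and a patient-level *and* is just cessation. Section 5.5 names two outcomes, section 3.0 lists (a) and (b), and section 5.6 models both, so a composite is unlikely. The 12-month wording, "The final secondary outcome is cessation, or 25% decrease of benzodiazepine use at 12 months", concerns a secondary outcome and does not settle the 6-month rule.

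**Conclusion.** The point holds. The missing success rule and the conflict between *and* and *or* can be read directly from the text and rest on no assumption.

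The size is conditional. If either outcome suffices at two-sided .05, the chance of at least one false rejection is about 6.4-9.5% against the stated 5%, and of a false claim of benefit about 3.2-4.8% against 2.5%. This rests on the assumed null rates and the unadjusted 6-month test; with control cessation of about 1% there is little or no excess. If both are required, the .05 is kept, but power is about 68-73% when each outcome alone has 80%. So one of the two stated figures, .05 or 80%, generally fails under each reading.

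If the .05 was meant as one-sided, false claims of benefit under the either-suffices reading would be 6.4-10.3%, against 4.7-6.1% for a single test in the same simulation.

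**What to change.** Use one wording in the Abstract, section 2.0 and section 3.0, with two separate hypotheses at six months. H1: the proportion who cease is higher with EMPOWER for Veterans than with control. H2: the proportion with a reduction of at least 25% is higher.

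Before outcome data by arm are seen, add one sentence to section 5.6: *H1 and H2 are tested with Holm's procedure at an overall two-sided .05.* If the sponsor confirms that *and* means both, write instead: *The trial succeeds only if H1 and H2 are both significant at two-sided .05.*

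State sidedness in section 5.1 and restate the power there for the chosen rule.

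The cost is text and some power. Under Holm, an outcome with 80% power at .05 has about 71-75% when tested at .025, while at least one outcome succeeds in 81-87%. At the plan's effect size of 0.35 with 66 per group (normal approximation, intra-class correlation ignored), moving one test from .05 to .025 lowers power from 52% to Φ(2.011 − 2.241) = 41%. No extra participants or procedures are needed.

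### Where only VHA data score the outcome (everyone at 12 months, and anyone without an interview at 6), death, leaving VA care or outside prescribing reads as cessation

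*Combined protocol and SAP*

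**What the plan says.** Section 5.5 (Study Evaluations) words cessation in two ways. The first is "Cessation will be defined as the absence of a benzodiazepine prescription renewal in the six months prior to follow-up". The second is "Cessation will be defined as an absence of a benzodiazepine prescription at the time of the 6-month follow-up", with the added condition that the absence has lasted at least three months. The windows differ and need reconciling, but both make the absence of a prescription event the criterion for success. On the source for benzodiazepine dose and use, the section says "These data will be obtained from the CDW", which section 5.1 identifies as VHA's centralized patient database.

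At 6 months a self-report TLFB is added, in part "to determine the existence of any additional benzodiazepine prescriptions (e.g., from a non-VHA provider". The section says both sources will be considered in deciding the outcome. It gives no rule for disagreement between them or for a missing TLFB. People who cannot be reached by phone are mailed the assessment, and then "Should the participant not respond to outreach efforts they will be considered lost to follow up".

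Of the 12-month benzodiazepine outcome the section says "this will be conducted using databases only", and no other 12-month outcome data are collected. The two primary outcomes are nested: "All participants who cease benzodiazepines entirely will be included in those who achieve 25% or more reduction".

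Section 5.6 (Data Analysis) fits one model to the 6- and 12-month outcomes and drops the arm-by-time interaction if it is not significant at 0.05. Missing values may be multiply imputed if missing at random is judged reasonable. Neither section says how death, leaving VA care or a change of prescriber is handled.

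**The concern.** When success is the absence of a record, anything that stops the record being made looks like success. A participant who dies, leaves VA care or gets benzodiazepines elsewhere stops generating VHA prescriptions. Applied literally, the algorithm returns a valid value of ceased, not a missing value, so the imputation provision in section 5.6 is never triggered. Through the nesting rule the same person is also a 25% reducer.

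If this happens equally in both arms, it adds false ceasers to each and pulls the odds ratio towards 1, most strongly when true cessation is uncommon. If it happens unequally, it can create or hide a difference. The 12-month result, meant to show whether effects last, is the most exposed because no second source exists there.

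**Working it through.** **Who is exposed.**

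| Time | Participant | Source | Exposed? |
|---|---|---|---|
| 6 months | TLFB completed | CDW and TLFB | Largely protected, though the combining rule is unstated |
| 6 months | No TLFB (died, unreachable) | CDW, if scored at all | Yes, if scored from the CDW |
| 12 months | Everyone | VHA databases only | Yes |

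**How many.** Section 5.1 (Sample Size) plans 85 per group, 170 in total, and 80% follow-up at 6 months. Without a 6-month assessment: 0.20 × 170 = 34, or 17 per arm. These are people whom the TLFB cannot check. They are not 34 false ceasers, since most may still have VA prescriptions. At 12 months all 170 rest on the databases.

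**Timing.** Under the three-month wording, a death or exit counts only if the prescription has been absent for three months by follow-up, so late events do not qualify. Under the six-month renewal wording the window is longer.

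**Route to the main effect.** Both primary outcomes are at 6 months and the 12-month outcome is secondary. However, the section 5.6 model contains both times. Once the interaction is dropped, a single arm coefficient pools them, so 12-month misclassification enters the estimate used for the primary comparison.

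**Illustration, equal loss.** The documents give neither cessation rates nor rates of loss from VA prescribing, so every input here except 85 per arm is assumed. Let p be true cessation (5% control, 15% EMPOWER) and m the share of non-ceasers in each arm lost to VA prescribing. The observed rate is p + (1 − p)m. For m = 2%:

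- control: 0.05 + 0.95 × 0.02 = 0.069
- EMPOWER: 0.15 + 0.85 × 0.02 = 0.167
- odds ratio: (0.167/0.833) ÷ (0.069/0.931) = 2.71
- false share of control ceasers: 0.019/0.069 = 28%

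| m | Control | EMPOWER | Risk difference | Odds ratio | False share, control | Power, 85 per arm |
|---|---|---|---|---|---|---|
| 0 | 5.0% | 15.0% | 10.0 pts | 3.35 | 0% | 59% |
| 2% | 6.9% | 16.7% | 9.8 pts | 2.71 | 28% | 51% |
| 4% | 8.8% | 18.4% | 9.6 pts | 2.34 | 43% | 45% |
| 6% | 10.7% | 20.1% | 9.4 pts | 2.10 | 53% | 40% |

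Power is for a two-sided 5% two-proportion comparison at one time point with everyone scored.

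**A second set of assumptions.** The planned effect size of 0.35 converts to an odds ratio of exp(0.35 × π/√3) = 1.89. With 10% control cessation that gives 17.3% on EMPOWER. Equal loss of 3%, 5% and 10% lowers the odds ratio to 1.70, 1.61 and 1.47.

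**Unequal loss, no true effect.** With 10% true cessation in both arms and loss of 10% on EMPOWER versus 5% on control, the observed rates are 0.10 + 0.90 × 0.10 = 19.0% and 0.10 + 0.90 × 0.05 = 14.5%, a spurious 4.5 points. The sign reverses if control loses more.

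**The case against.** The strongest reply is that the plan anticipates the problem. The TLFB is collected partly to find non-VHA prescriptions, and both sources inform the 6-month outcome. That stands. A reader might infer that moving to an outside prescriber counts as success for everyone at 6 months. The documents do not support this for anyone who completes the TLFB and reports the use.

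Nor does the plan state that death counts as success. That follows from a literal definition plus silence. People who do not respond are called lost to follow-up, and the sample size allows for 20% loss, so they may well be meant to be missing at 6 months. The text does not settle this, because a CDW outcome can be computed without an interview. At 12 months that reading is not available, since no interview is planned.

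The illustration is also open to challenge. On the risk-difference scale little changes, and power falls less when the true contrast is larger. Screening on a recent primary care visit, requiring a designated VA primary care provider and excluding palliative patients should all reduce deaths and exits. Finally, a reader might infer that the result is biased in a known direction. Nothing in the documents points to unequal loss between arms, so that remains a possibility only.

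**Conclusion.** The concern holds for all participants at 12 months, and at 6 months for anyone without a TLFB who is scored from the CDW. For them the literal rule scores death, leaving VA care or a move to an outside prescriber as cessation and hence as a 25% reduction. The 12-month errors also feed the pooled arm effect if the interaction is dropped. Participants with a completed 6-month TLFB are largely protected; what is missing for them is a written rule for combining the two sources.

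The size cannot be established from the documents. Under the assumed 5% versus 15% cessation and equal loss of 2% to 6% of non-ceasers, the relative effect is noticeably diluted while the absolute difference falls by at most 0.6 points. The point deserves correction because it is a foreseeable misclassification and cheap to prevent, not because a large bias has been shown.

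**What to change.** Amend sections 5.5 and 5.6 before outcomes are coded:

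1. At both times, score cessation from the CDW only if the participant is alive at the end of the window and has at least one VA encounter or VA fill of any drug within it. Apply the same check to any 25% reduction credited through cessation.
2. Do not score deaths as cessation, and state how they enter the analysis.
3. At 6 months, let outside benzodiazepine use reported on the TLFB override absence in the CDW. State what happens when the TLFB is missing.
4. Class people with no VA activity as unverified, not ceased. Anyone with a VA benzodiazepine fill passes the activity check, so only apparent ceasers can become unverified. Imputation under missing at random is therefore not enough alone. Report bounding analyses that count all unverified cases as not ceased and then all as ceased.
5. Report deaths and unverified cases by arm at 6 and 12 months.
6. State as a limitation that at 12 months outside prescribing to people still in VA care cannot be detected. The activity check does not solve this.

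The cost is some SAP wording and a few more database fields. Section 5.1 already uses the CDW to identify eligible patients; whether it holds vital status is not stated and should be confirmed. No extra patient contact is needed. The downside is a slightly lower apparent cessation rate and a few cases left unverified.
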